5. TREATMENT PLAN

This is a phase II, open-label, single arm, single-stage study. Both, chemo-sensitive and chemo-resistant patients will be enrolled and treated with 4 cycles of combination of Guadecitabine and carboplatin as detailed in the study schema. Premedication and hydration will be provided as per institutional standards for administration of carboplatin.

5.1 Drug Administration

Drug	Dose ¹	Route	Schedule ²	Cycle Length
Guadecitabine	30 mg/m^2	Subcutaneously (SC)	Days 1-5	4 weeks
Carboplatin	AUC 4	Intravenously (IV)	Day 5	(28 days)

¹ Body surface area (BSA) should be recalculated when weight changes based on institutional guidelines 2 A window of \pm 3 days may be applied to all Day 1 and 5 visits to accommodate observed holidays, inclement weather, scheduling conflicts etc. Date and time of each drug administration should be clearly documented in subject's chart and electronic case report forms (eCRFs).

5.2 Concomitant Medications

5.2.1 Allowed Concomitant Medications

All treatments that the investigator considers necessary for a subject's welfare may be administered at the discretion of the investigator in keeping with the community standards of medical care.

5.2.2 Prohibited Concomitant Medications

Drug-drug interaction studies have not been conducted with guadecitabine. *In vitro* studies suggest guadecitabine is unlikely to inhibit or induce human cytochrome p450 (CYP) enzymes and is not a substrate for CYPs, indicating that CYP-mediated drug-drug interactions with guadecitabine are unlikely to occur. Neither guadecitabine, nor the active metabolite decitabine inhibit major human drug transporters. Therefore, no specific concomitant medications are prohibited.

5.3 Supportive Care

Institutional standards should be followed for supportive care such as symptom management, hydration and transfusions. Filgrastim should be utilized based on NCCN guidelines.

Version Date: 18MAR2020 Confidential Page 14 of 41

5.4 Contraception

The following restrictions apply while the patient is receiving study treatment and for the specified times before and after:

Female patient of child-bearing potential

• Females of childbearing potential who are sexually active with a non-sterilized male partner must use at least 1 highly effective method of contraception from the time of screening and must agree to continue using such precautions for 180 days after the last dose of durvalumab + guadecitabine. Non-sterilized male partners of a female patient must use male condom plus spermicide throughout this period. Cessation of birth control after this point should be discussed with a responsible physician. Not engaging in sexual activity for the total duration of the drug treatment and the drug washout period is an acceptable practice; however, periodic abstinence, the rhythm method, and the withdrawal method are not acceptable methods of birth control. Female subjects should also refrain from breastfeeding throughout this period.

Male subjects with a female partner of childbearing potential

- Non-sterilized males who are sexually active with a female partner of childbearing potential must use a male condom plus spermicide from screening through 180 days after receipt of the final dose of durvalumab + guadecitabine or. Not engaging in sexual activity is an acceptable practice; however, occasional abstinence, the rhythm method, and the withdrawal method are not acceptable methods of contraception. Male subjects should refrain from sperm donation throughout this period.
- Female partners (of childbearing potential) of male subjects must also use a highly effective method of contraception throughout this period.

Females of childbearing potential are defined as those who are not surgically sterile (i.e., bilateral tubal ligation, bilateral oophorectomy, or complete hysterectomy) or post-menopausal.

Women will be considered post-menopausal if they have been amenorrheic for 12 months without an alternative medical cause. The following age-specific requirements apply:

- Women <50 years of age would be considered post-menopausal if they have been amenorrheic for 12 months or more following cessation of exogenous hormonal treatments and if they have luteinizing hormone and follicle-stimulating hormone levels in the post-menopausal range for the institution or underwent surgical sterilization (bilateral oophorectomy or hysterectomy).
- Women ≥50 years of age would be considered post-menopausal if they have been amenorrheic for 12 months or more following cessation of all exogenous hormonal treatments, had radiation-induced menopause with last menses >1 year ago, had chemotherapy-induced menopause with last menses >1 year ago, or underwent surgical sterilization (bilateral oophorectomy, bilateral salpingectomy or hysterectomy).

Highly effective methods of contraception, defined as one that results in a low failure rate (i.e., less than 1% per year) when used consistently and correctly are described in the table below. Note that some contraception methods are not considered highly effective (e.g. male or female condom with or without spermicide; female cap, diaphragm, or sponge with or without

Version Date: 18MAR2020 Confidential Page 15 of 41

spermicide; non-copper containing intrauterine device; progestogen-only oral hormonal contraceptive pills where inhibition of ovulation is not the primary mode of action; and triphasic combined oral contraceptive pills).

Highly Effective Methods of Contraception (<1% Failure Rate)

Barrier/Intrauterine methods	Hormonal Methods
Copper T intrauterine device	Etonogestrel implants: e.g. Implanon
Levonorgestrel-releasing intrauterine	Intravaginal device: e.g. ethinylestradiol
system (e.g., Mirena®) ^a	and etonogestrel
	Medroxyprogesterone injection: e.g.
	Depo-Provera
	Normal and low dose combined oral contraceptive pill
	Norelgestromin/ethinylestradiol
	transdermal system

a This is also considered a hormonal method

6. TOXICITIES AND DOSE DELAYS/DOSE MODIFICATIONS

The NCI Common Terminology Criteria for Adverse Events (CTCAE) v5.0 will be used to grade adverse events. Subjects enrolled in this study will be evaluated clinically and with standard laboratory tests before and at regular intervals during their participation in this study as specified in Study Calendar & Evaluations. Subjects will be evaluated for adverse events (all grades), serious adverse events, and adverse events requiring study drug interruption or discontinuation as specified in Study Calendar & Evaluations.

6.1 Dose Delays/Dose Modifications

Unless otherwise noted in the dose modification tables below, treatment may be delayed ≤ 2 weeks from the expected day of the next treatment for any reason. If treatment is delayed ≥ 2 weeks, subjects will proceed with the next cycle of treatment at the dose level recommended according to the tables below.

6.2 Dose Levels for Dose Reductions

Dose level	Dose of carboplatin	Dose of Guadecitabine
Starting Dose	AUC 4	30mg/m^2
Dose level (-1)	AUC 4	24mg/m ²

Version Date: 18MAR2020 Confidential Page 16 of 41

Dose Modification Guidance Table (applies to Day 1 for all cycles except for Cycle 1)

Neutropen	Neutropenia (absolute neutrophil count [ANC])			
Toxicity	Grade	Stipulations	Suggested Action	
	G3 500 - 999/mm ³ (w/out fever [>38.3°C or 101.0°F])	≤ 14 days of interruption/delay	 hold treatments until ANC >1000/mm³ Prophylaxis with granulocyte colony stimulating factor (G-CSF) starting with next cycle should be considered by treating physician. In these patients GCSF support will be given on Day 6 through an on-body injector (neulasta onpro) no change in Guadecitabine or carboplatin dose 	
	G3 500 - 999/mm ³ (w/out fever)	> 14 days of interruption/delay	 hold treatments until ANC >1000/mm³ Prophylaxis with granulocyte colony stimulating factor (G-CSF) starting with next cycle should be considered by treating physician. In these patients GCSF support will be given on Day 6 through an on-body injector (neulasta onpro) reduce Guadecitabine by one dose level 	
	G3 500 - 999/mm ³ (w/ fever)		 hold treatments until ANC >1000/mm³ Prophylaxis with granulocyte 	
	G4 (w/out fever)	Lasting ≤ 14 days	 Prophylaxis with grandrocyte colony stimulating factor (G-CSF) starting with next cycle should be considered by treating physician. In these patients GCSF support will be given on Day 6 through an on-body injector (neulasta onpro) reduce Guadecitabine by one dose level 	
Any episode	G4 (w/out fever)	G4 lasting > 14 days	discontinue subject from study	

Version Date: 18MAR2020 Confidential Page 17 of 41

Thrombocytopenia			
Toxicity	Grade	Suggested Action	
1	G3 25,000 - 50,000/mm ³	 hold treatments until plt ≥ 50,000/mm³ reduce Guadecitabine by one dose level 	
	$G4 < 25,000/\text{mm}^3$	discontinue subject from study	

6.3 Protocol Therapy Discontinuation

In addition to discontinuation from therapy related to toxicities as outlined above, a subject will also be discontinued from protocol therapy and followed per protocol under the following circumstances outlined below. The reason for discontinuation of protocol therapy will be documented on the electronic case report form (eCRF)

- Documented disease progression.
- Site investigator determines a change of therapy would be in the best interest of the subject
- Subject requests to discontinue protocol therapy, whether due to unacceptable toxicity or for other reasons
 - In a subject decides to prematurely discontinue protocol therapy ("refuses treatment"), the subject should be asked if he or she may still be contacted for further scheduled study assessments. The outcome of that discussion should be documented in both the medical records and in the eCRF.
- Female subject becomes pregnant
- Protocol therapy is interrupted for ≥ 6 weeks.

6.4 Protocol Discontinuation

If a subject decides to discontinue from the protocol (and not just from protocol therapy) all efforts should be made to complete and report study assessments as thoroughly as possible. A complete final evaluation at the time of the subject's protocol withdrawal should be made with an explanation of why the subject is withdrawing from the protocol. If the reason for removal of a subject from the study is an adverse event, it will be recorded on the eCRF.

Version Date: 18MAR2020 Confidential Page 18 of 41

7. STUDY CALENDAR & EVALUATIONS

Study Evaluation Cycle = 28 days	Screening	On Treatment Cycle 1-4		Safety follow up visit ⁹	Long-term Follow up ¹⁰
	-28 days	Day 1 ± 3 days	Day 5 ± 3 days	30 days post last dose (± 7 days)	Every 2 months (±14 days)
REQUIRED ASSESSMENTS					
Informed Consent	X				
Medical History ¹	X				
Physical Exam	X	X		X	
Vital signs and ECOG Performance Status ²	X	X	X	X	
AEs & concomitant medications	X	X	X	X	
LABORATORY ASSESSMENTS					
Complete Blood Cell Count with diff (CBC)	X	X^8	X	X	
Comprehensive Metabolic Profile (CMP)	X	X^8	X	X	
Pregnancy test (urine or serum) (WOCBP) ³	X				
DISEASE ASSESSMENT					
CT or PET CT of chest ⁴	X	Prior to C3D1		X	X
CT, PET CT or MRI of abdomen and pelvis ⁴	X	Prior to C3D1		X	X
Bone Scan ⁴	X	Prior to C3D1		X	X
TREATMENT EXPOSURE					
Guadecitabine		Daily l	D1-D5		
Carboplatin			X		
SPECIMEN COLLECTION					
Archival Tumor Tissue or Fresh Tissue ⁵	X^5	X ⁵	C2D5	X	
Whole blood for somatic baseline and CTCs ⁶		C1D1			
Whole blood for PBMCs ⁶		C1D1	C2D5	X	
BANKING SAMPLES					
Whole blood ⁷		C1D1			
Whole blood for plasma and serum ⁷		C1D1		X	
FOLLOW-UP					
Survival Status, Subsequent Therapy					X

CBC with differential and platelet to include: WBC, ANC, Hgb, Hct, PLT. CMP to include sodium, potassium, chloride, creatinine, blood urea nitrogen; liver function tests (LFTs) to include AST, ALT, total bilirubin, alkaline phosphatase and LDH

Key to Footnotes

- 1: Medical History; other data to obtain during this assessment includes: diagnosis and staging to include pathology report and staging documentation. A smoking history questionnaire and trial awareness question. Prior anti-cancer treatment should be documented including medications (chemotherapy, checkpoint inhibitors, etc) radiation or surgery.
- 2: Vital signs to include blood pressure, temperature, pulse, oxygen saturation, weight, and height (screening only) and ECOG performance status.
- 3: For women of childbearing potential (WOCBP): urine or serum βhCG if clinically appropriate. If a urine test is done and it is positive or cannot be confirmed as negative, a serum pregnancy test will be required. Testing is required at screening.
- 4: Tumor response assessment will consist of evaluation by CT or PET CT scan of chest. An MRI, CT or PET CT scan of the abdomen and pelvis may be done if there is measurable disease that is not detectable by CT or PET CT of the chest. A bone scan may be used for subjects with bone only disease or if there is suspicion of bone metastasis. Imaging will be performed at screening, prior to Cycle 3 and at the D30 safety follow up visit (± 7 days). Imaging selected for each subject should remain the same throughout the study. If tumor assessments are available for subjects who have not yet experienced progressive disease (PD) at the time treatment is discontinued, the follow-up tumor evaluations will be documented in the eCRF until PD or death is confirmed, or until another treatment is initiated.
- 5: Archival tissue is required if available and should be identified at screening and shipped by C2D1. If archival tissue is not available, subjects may still be eligible. Biopsies will be obtained prior to C1D1 from 15 patients with easily accessible disease regardless of availability of archival tissue. These same 15 patients will be required to undergo a repeat biopsy prior to treatment on C2D5 if clinically feasible. These same subjects will have the option to undergo a biopsy at progression/safety visit. See Correlative Laboratory Manual (CLM) for detailed instructions.
- 6: Whole blood will be collected for somatic baseline and CTCs prior to treatment C1D1. Whole blood will be collected prior to treatment C1D1, C2D5 and at progression/Safety Follow Up visit for isolation of peripheral blood mononuclear cells. See CLM for detailed instructions.
- 7: Samples for banking for future unspecified cancer related research include: Whole blood: collected prior to treatment on Cycle 1 Day 1. Whole blood for Serum and Plasma: collected prior to treatment on Cycle 1 Day 1 and at the 30-day Safety Follow-up visit. See CLM for detailed instructions.

Version Date: 18MAR2020 Confidential Page 20 of 41

- 8: CBC and CMP to be performed during screening for eligibility and on C1D1 prior to treatment. For the remainder of the Cycles, CBC and CMP may be performed within 4 days prior to Day 1 of treatment.
- 9: The safety follow-up visit should only occur when subjects permanently stop study treatment for whatever reasons (toxicity, progression, or at discretion of site investigator) and should be performed 30 days (± 7 days) after the last dose of treatment. Subjects who have an ongoing Grade ≥ 2 or serious AE (SAE) at this visit will continue to be followed until the AE resolves to ≤ Grade 1 or baseline, deemed clinically insignificant, and/or until a new anti-cancer treatment starts, whichever is earlier.
- 10: Long-term follow up will occur in all subjects until documented disease progression. Radiology imaging should be performed every 2 months (± 7 days). Subjects who discontinue treatment for any reason without documented disease progression will be followed every 2 months for 1 year (± 14 days). Once disease progression is documented, subjects will enter a survival follow up period every 3 months for 1 year from the time of documented progression. Follow up may be accomplished via clinic visit, phone call, or other avenues as appropriate.

Version Date: 18MAR2020 Confidential Page 21 of 41

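### The one on-treatment scan, due before Cycle 3, has no latest calendar date, so in a few patients with long dosing delays it can fall after the 3-month test point

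*Combined protocol and SAP*

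**What the plan says.** Section 7, footnote 4: "Imaging will be performed at screening, prior to Cycle 3 and at the D30 safety follow up visit (± 7 days". The 7-day tolerance belongs to the safety visit. The calendar rows for imaging also name only the cycle.

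Dosing delays are governed by three places:

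- Section 6.1 counts delay "from the expected day of the next treatment for any reason" and ordinarily allows up to 2 weeks. It then adds: "If treatment is delayed ≥ 2 weeks, subjects will proceed with the next cycle of treatment", at the dose level given in the tables.
- Section 6.2 has a Grade 3 neutropenia row for "> 14 days of interruption/delay", which leads to a dose reduction and not to stopping. The Grade 3 thrombocytopenia row says "hold treatments until plt ≥ 50,000/mm³" and gives no time limit.
- Section 6.3 ends treatment when "Protocol therapy is interrupted for ≥ 6 weeks". It does not say whether the 6 weeks run from the expected day or from the last dose, and no rule limits the sum of several delays.

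No other scheduled imaging covers a patient on hold. The safety visit (footnote 9) takes place only after a permanent stop, and the 2-monthly imaging (footnote 10) belongs to long-term follow-up. Section 12.6.1 compares PFS in the chemo-sensitive group with 3 months by a one-sided sign test for censored data.

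**The concern.** The sign test depends on which side of 3 months each event is dated. PFS ends when progression criteria are met, which in practice is often the date of a scan. If a patient's first post-baseline scan comes after Day 92, progression that occurred earlier and was not found clinically or on an unscheduled scan counts as PFS beyond 3 months. The error has one direction, towards rejecting the null. The plan has no rule for late scans or for progression known only to lie between two scans.

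**Working it through.** **The plan's own figure.** Section 12.3 gives 80% power for n = 24, one-sided 0.10, median 3 against 6 months. Under exponential PFS, S(3 months) is 0.5 against 0.5^(3/6) = 0.707. The critical proportion is 0.5 + 1.2816 × 0.5/√24 = 0.631, and the SD under the alternative is √(0.707 × 0.293/24) = 0.0929. Power = Φ((0.707 − 0.631)/0.0929) = 79.4%, so the stated figure is reproduced. The exact sign test needs 16 or more of 24 beyond 3 months: size 0.076, power 0.751 (a cut-off of 15 has size 0.154).

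**When the scan passes month 3.** Month 3 is 1 + 3 × 30.4375 = Day 92.3. With 28-day cycles, Cycle 3 Day 1 is Day 57, so the delay needed is 93 − 57 = 36 days.

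| Route | Cycle 3 Day 1 |
|---|---|
| Two 14-day delays | 57 + 28 = Day 85 (before month 3) |
| One hold of 36-41 days, counted from expected day | Day 93-98 |
| 14-day hold then 22-day hold, counted from expected day | 29 + 14 = 43; 43 + 28 + 22 = Day 93 |
| Last-dose count, one maximal hold (41 − 24 = 17 days) | Day 74 |
| Last-dose count, two maximal holds | 57 + 34 = Day 91 |
| Same, with +3 days on both Day 5 visits | 8 + 41 = 49; 49 + 7 = 56; 56 + 41 = Day 97 |

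The 14 + 22 route needs only one dose reduction. On a last-dose count, month 3 is passed only with near-maximal holds plus the Day 5 windows.

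**Size.** Take true median PFS 3 months, exponential, with F(d) = 1 − 2^(−(d−1)/91.31): F(57) = 0.346, F(71) = 0.412, F(90) = 0.491. Let q be the share of progressions dated at their true time (assumed 0.5). The chance of being recorded beyond 3 months is 0.5 + (1 − q)(0.5 − F(scan)) if the scan precedes month 3, and 0.5 + (1 − q) × 0.5 otherwise:

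- scan Day 57: 0.577
- scan Day 71: 0.544
- scan Day 90: 0.504
- scan after month 3: 0.750

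Assume 30% of patients have one 14-day hold (scan Day 71) and a fraction L have a total delay of 36 days or more. False-positive rate = P(X ≥ 16 of 24):

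- L = 0: 0.70 × 0.577 + 0.30 × 0.544 = 0.567, rate **0.219**
- L = 2% (0.5 patients), all scans deferred: 0.570, rate **0.230** (+0.010)
- L = 5% (1.2 patients), all scans deferred: 0.65 × 0.577 + 0.30 × 0.544 + 0.05 × 0.750 = 0.576, rate **0.245** (+0.026)
- Half of those scans deferred, the rest done on Day 57: 0.224 and 0.232 (+0.005 and +0.013)

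Varying q, with all scans deferred and L = 0, 2%, 5%:

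- q = 0.25: L = 0 gives 0.70 × 0.615 + 0.30 × 0.566 = 0.600; rates 0.330, 0.349, 0.378
- q = 0.75: L = 0 gives 0.70 × 0.538 + 0.30 × 0.522 = 0.533; rates 0.135, 0.138, 0.144

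**With a Day 90 limit (q = 0.5).** Replacing 0.750 by 0.504 for the long-delay patients gives 0.215 (2%) and 0.209 (5%).

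**For scale.** With no delays at all, every scan is on Day 57 and the rate is 0.249. The next scheduled scan is then the safety-visit scan, which "should be performed 30 days (± 7 days) after the last dose of treatment": Cycle 4 Day 5 is Day 89, so about Day 119 (Day 112-126).

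**The case against.** The strongest reply is that the case is rare and that delay alone does not produce it. This largely stands.

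- Section 6.1 normally limits delay to 2 weeks, so longer holds come mainly from the haematology tables. Grade 4 neutropenia beyond 14 days and Grade 4 thrombocytopenia end participation, and a long Grade 3 neutropenia hold brings a dose reduction and consideration of G-CSF.
- A reader might infer that any two moderately long holds suffice, for example 18 days each. Under the tables each such hold calls for a guadecitabine reduction, and section 6.2 offers only one reduced level, so the second hold has no dose to resume at.
- The scan need not slip. Under footnote 8, "CBC and CMP may be performed within 4 days prior to Day 1 of treatment", so the scan may already be done when a hold before Cycle 3 is called. Unscheduled scans are not barred, and deaths are dated exactly. A long hold before Cycle 2 is different, because the whole pre-Cycle 3 visit moves with it.
- The hold rates and the share of progressions dated truly are assumptions, and the model is an uncensored binomial whereas the plan specifies a sign test for censored data.

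What remains is that no text sets a latest date for the scan, and that total delays of 36 days or more are permitted.

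**Conclusion.** The point holds as a minor one. The scan before Cycle 3 has no latest date, and where total delay reaches 36 days and the scan is deferred, earlier progression can be recorded as PFS beyond 3 months. On the assumed inputs the false-positive rate rises by about 0.01-0.03, or about half that if half the scans are deferred. If everyone else's progression were dated perfectly, the exact size would move from 0.076 to 0.083 (L = 2%: 0.98 × 0.5 + 0.02 × 0.75 = 0.505) or 0.095 (L = 5%: 0.5125), still under 0.10.

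Three stronger readings are not supported:

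- That delays in general favour the drug. Delays up to 35 days bring the scan closer to month 3 and improve detection: 0.219 with 30% short holds against 0.249 with none.
- That rates of 0.23-0.25 are caused by late scans. Most of that comes from the on-schedule gap between Day 57 and about Day 119.
- That the full fall under a Day 90 limit (0.230 − 0.215 = 0.015; 0.245 − 0.209 = 0.037 by unrounded values) measures the harm. Part of it arises because Day 90 is a better scan date than Day 57, which is also why the scan should not be fixed at Day 57.

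The timing of the safety visit after a stop under the 6-week rule is a separate scheduling detail and forms no part of this point.

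**What to change.** In footnote 4 and the calendar imaging rows, write: *prior to Cycle 3 and in any case no later than Day 90, whether or not the cycle is on hold*. Dosing, holds and stopping rules stay as they are.

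The cost is a wording amendment. Scan dates do not change for delays up to 33 days (57 + 33 = Day 90) and move 1-2 days earlier for delays of 34-35 days. There are two downsides:

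- After a very long hold, Cycle 3 may start on an older scan: 3-8 days old after one hold of 36-41 days, and in the extreme of two 41-day holds (Day 139) 49 days.
- A patient held before Cycle 3 who then stops on the 6-week rule (57 + 42 = Day 99, expected-day count) may have one extra scan close to the safety-visit scan, so the change is not wholly free of added imaging.

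The on-schedule gap stays open. An added scan by Day 90 for every patient would address it (0.082 in the same model) and would also cover this point.
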